ATRIAL FIBRILLATION AND LONG-TERM ECG MONITORING OF HEART RHYTHM IN THE TROMSØ STUDY

Atrial fibrillation (AF) is common and increases the risk of mortality, stroke, heart failure and cognitive impairment. AF imposes significant burden to patients and their families, including reduced life years, health related quality of life, societal health and health economy. One of three AF cases are undiagnosed. Several methods for detection of AF exist, but most of them have major limitations and are associated with resource-demanding diagnostic workup in specialist health care services. This randomized clinical trial will evaluate whether self-screening for AF in patients with increased levels of NT-proBNP utilizing a novel Norwegian patch ECG sensor a) reduces AF-related morbidity and mortality in a well-defined cohort and b) identify factors related to individual risk. Identification of individuals at risk and patient-centered early diagnosis through screening can facilitate a personalized preventive health care approach to improve individual physical health and life quality.

1. EXCELLENCE

1.1. STATE OF THE ART, KNOWLEDGE NEEDS AND PROJECT OBJECTIVES

Atrial fibrillation (AF) is the most common cardiac arrhythmia, affecting more than 33 million people worldwide.¹ AF increases the risk of ischemic stroke (IS), premature death, heart failure and cognitive impairment and provokes significant societal and health economic burden.² The prevalence of AF increases with age, reaching from <1% in people aged < 40 years to between 10% and 17% in those aged > 80 years, with a higher prevalence in men than in women.³ Known risk factors for developing AF include male gender, age, previous heart disease, hypertension, smoking, alcohol consumption and obesity.⁴ Future projections suggest that the burden of AF may increase by >60% in 2050,⁵ due to ageing populations and increase in major AF risk factors such as obesity, inactivity, and underlying cardiovascular diseases (CVD).¹ Up to one third of AF cases are undiagnosed due to the intermittent and often asymptomatic nature of AF.^{6,7}

Studies have shown that 20-30% of all strokes are attributed to AF and that AF confers a 2-10 fold increased risk of stroke dependent on age and presence of other risk factors.^{7,8} AF related stroke is particularly debilitating and potentially lethal because the size of embolism that is caused by a left atrial thrombus may lead to obstruction of larger cerebral arteries.⁹ A recent estimation from Sweden calculated 5000 yearly strokes due to AF in Sweden with an estimated annual cost of 7,4 billion SEK.¹⁰ AF is also associated with an up to a 30% increased risk of developing dementia¹¹, independent of clinical stroke events.¹² Cognitive impairment in AF is likely related to micro-embolic events resulting in subclinical brain lesions (revealed by neuroimaging techniques).¹² However, prior research has reported inconsistent findings on the association between AF and morphological changes linked to dementia detected by brain MRI, such as subclinical cerebral infarction, brain atrophy and white matter hyperintensities.^{13,14}

Anticoagulation treatment reduces the risk of IS by 70% in patients with AF and may potentially prevent premature death and cognitive impairment.⁷ As a large proportion of AF episodes remain asymptomatic¹⁵, timely diagnosis of AF remains a major challenge in clinical practice and oral anticoagulant therapy is often initiated only after a stroke.¹⁶ Early diagnosis and initiation of anticoagulant treatment is key to prevent mutilating stroke sequelae. The diagnosis of AF is made by recording the heart rhythm with an electrocardiogram (ECG). The ECG can be a single recording, intermittent recordings, or continuous recording for hours or days, and several types of devices for ECG monitoring exist. In patients with intermittent (paroxysmal) AF, the diagnosis is often missed by single or repeated ECG recordings, while prolonged continuous ECG-monitoring improves the detection rate.¹⁷ Long-term assessment of the heart rhythm is usually performed by a conventional Holter monitor system which requires a recording device coupled to electrodes on the chest.¹⁸ Although an important diagnostic improvement when implemented in the 1960ies, the Holter monitoring system usually features brief testing intervals (24-72 hours), is susceptible to

disruptions and have high operational expenses. Because of the latter, there is a scarcity of these devices in numerous hospitals, which frequently results in lower utilization rates than recommended, and consequently extensive waiting lists.¹⁹ Other devices for AF-detection include thumb-ECG devices (TED) and implantable loop recorders (ILR). TEDs have been used in previous cohort studies and AF screening studies, but have limited heart rhythm monitoring time and consequently lower sensitivity to intermittent arrhythmias.^{20,21} ILRs have also been used in a previous AF screening study⁵ and allow for continuous rhythm monitoring over years, but require surgical procedures. Watches with heart rate monitoring based on arterial pressure waves cannot be used for clinical diagnostics.⁷ Another alternative is patch ECG-devices, which in smaller studies have been shown to be well suited for AF screening.²²⁻²⁴

AF fulfils most criteria for population screening; a severe and prevalent health problem that can be asymptomatic and for which highly effective treatment exists.²⁵ Systematic rhythm monitoring can enable earlier detection of AF and initiation of anticoagulant therapy.^{26,27} Yet, the cost-effectiveness of AF screening is not settled.²⁸ In the recently published STROKESTOP trial, a strategy with AF screening by TED twice daily for 2 weeks was found to reduce the composite primary outcome (stroke, systemic embolism, bleeding leading to hospitalization and all-cause death) by 4% and the risk of IS by 8%.²¹ In the Danish LOOP study, AF screening with ILR resulted in a three-times increase in the number of AF patients detected and anticoagulation initiated and a 20% reduction in the risk of stroke or systemic arterial embolism during follow-up, which did not reach statistical significance (HR 0.80; 95% CI 0.61–1.05; p=0.11).²⁹ The European Society of Cardiology recommends screening for AF in people >75 years of age and in patients with increased risk of stroke, but gives no clear recommendations for method and frequency.⁷

The CHA₂DS₂-VASc risk score is based on age and traditional CVD risk factors and is currently used to predict the risk of IS among patients with AF and guide initiation of anticoagulant treatment. The score's predictive accuracy is however modest, with a C-statistic of ~0.6 for prediction of thromboembolism.^{30,31} N-terminal pro-B-type natriuretic peptide (NT-proBNP) has emerged as a promising biomarker to improve risk prediction. Previous studies have shown that NT-proBNP is elevated in patients with AF and associated with the risk of stroke.³² Data from several randomized trials showed that adding NT-proBNP to the CHA₂DS₂-VASc score significantly improved the prediction of stroke in patients with AF.³²⁻³⁴

The STROKESTOP II study investigates the potential of NT-proBNP as a stratification tool to improve efficacy of AF screening in a randomized population-based study.³⁵ High and low risk groups were defined according to a cutoff of NT-proBNP $\geq 125\text{ng/L}$. New AF was detected in 2.6% of all patients and 4.4% in the high risk group. A recent subgroup analysis from the randomized LOOP study³⁶ suggests that in an older population with additional stroke risk factors, ILR screening is associated with a significant reduction in stroke risk among participants with baseline NT-proBNP above median but not among those having lower levels.³⁶ These results support the potential of NT-proBNP to improve the benefit of AF screening and possibly aid in risk stratification for preventive treatment. However, the utility of NT-proBNP for targeting AF screening and prevention of AF consequences needs to be addressed in well-designed randomized trials.

The risk of IS in patients with AF is presumed to arise from emboli generated by structural and functional alterations within the atria, where a pro-thrombotic milieu is established, particularly in the left atrial appendage.³⁷ Consequently, a new concept of atrial cardiomyopathy has evolved, defined by complex structural, functional and electrophysiological changes, affecting the atria with the potential to produce clinically relevant manifestations.³⁸ Several transthoracic echocardiographic parameters have emerged as promising biomarkers of AF. These include left arterial volume and left arterial function assessed by strain which are associated with AF in patients at risk^{39,40} and in patients with IS of undetermined source.^{41,42} However, knowledge of association between echocardiographic parameters and paroxysmal AF in a general population is limited.

Previous studies report that AF is associated with poor health-related quality of life (HRQoL). However, the factors influencing HRQoL in patients with AF are not well understood. A literature review from 2019⁴³ concluded that patients with AF had consistently lower HRQoL than healthy individuals and patients with other cardiovascular diseases. The most common factor associated with HRQoL in patients with AF was anxiety-specific. This may be related to both to the increased burden of disease associated with AF and to fear of complications from treatment.^{44,45} Effects of AF screening on HRQoL is scarcely mapped and highly relevant when considering the benefits of population based screening.

Several knowledge gaps still exist regarding risk stratification, effectiveness, implementation and outcomes of screening programs for AF. Evidence on optimal screening methods in terms of accuracy, cost-effectiveness and feasibility is lacking. Identification of individuals to target for AF screening is essential and the optimal approach to risk stratification for screening purposes remain unclear. Impact of AF screening on clinical outcomes such as stroke prevention, mortality reduction, cognitive function and quality of life is not fully understood and more evidence is needed to assess the long-term effects on patient outcomes, including potential harms associated with overdiagnosis and overtreatment. Subclinical AF refers to episodes of atrial arrhythmia that are asymptomatic and may only be detected through continuous monitoring. It's unclear whether the detection and treatment of subclinical AF lead to improved outcomes compared to clinical AF or if it carries a similar risk of complications such as IS.

The present project is planned as a sub-study of the epidemiological population-based Tromsø Study. In a randomized controlled clinical trial, we plan to test the primary hypothesis that in individuals with elevated NT-ProBNP who are diagnosed with AF through long-term ECG monitoring, anticoagulation treatment according to international guidelines will reduce the incidence of stroke and cardiovascular death in the screening group compared to individuals who do not undergo screening (control group). The study will be performed within a well-defined cohort with extensive available longitudinal and cross-sectional information on risk factors and co-existing conditions. This setup facilitates addressing several knowledge gaps concerning risk stratification including associations between AF and echocardiographic parameters, cognitive impairment, structural changes on brain MRI, and HRQoL.

1.2. NOVELTY AND AMBITION

This project has the potential for providing new knowledge related to the benefit of a stepwise screening approach for AF according to NT-proBNP level, utilizing a novel patch monitor with continuous ECG monitoring and automatic artificial intelligence based (AI) ECG analysis. It can contribute to the identification of a population that is more likely to benefit from AF screening and address the usefulness of CHA₂DS₂-VASc and other novel biomarkers including echocardiographic parameters in the current risk factor era.

The Tromsø Study is an internationally recognized and leading epidemiological study. Data collection includes questionnaires, medical interviews, blood tests and comprehensive clinical examinations with echocardiography, respiratory testing, cognitive testing and MRI of the brain.^{46,47} Many participants have attended previous surveys of the Tromsø Study and thus repeated measures are available for several individuals. This approach enables us to identify individual phenotypes with increased risk of AF and AF complications. Information on incident stroke, myocardial infarction, and cause-specific deaths in the participants are obtained through annual linkage to the national registries (the Norwegian Stroke Registry, the Norwegian Myocardial Infarction Registry and the Causes of Death Registry). The combination of clinical data including imaging data with the extensive data collection on both exposure and outcome variables and cross-links between the various sub-projects of the Tromsø Study provides a rich datasource for research, with the potential for several future PhD and postdoc-projects.

Our project group collaborates with major projects within the national AFIB network investigating different aspects related to AF screening and risk stratification. Outcomes in the proposed study are harmonized with these projects, enabling data merging to address central knowledge gaps in larger datasets.

The project focuses on addressing challenges on the path towards a user-centered and sustainable healthcare service through collaboration and use of new technology. The project will provide new knowledge on the utility of novel diagnostic tools for continuous ECG monitoring analyzed with AI based algorithms with high sensitivity and specificity and whether this tool can simplify AF screening, and may thus impact future planning of AF screening. Through the project we will identify biomarkers that would allow stratification of individuals with respect to screening, medical treatment, enable individual precision-based medicine, and ultimately reduce stroke events, with great benefit to patients and the health care system.

1.3. RESEARCH QUESTIONS AND HYPOTHESES, THEORETICAL APPROACH AND METHODOLOGY

The significance and originality of the proposal:

We propose to perform a randomized controlled screening trial within the Tromsø 8 population-based cohort study, applying monitoring of heart rhythm with leading sensor technology (ECG247) in participants with elevated levels of NT-proBNP. We will add important data to ongoing screening trials by including comprehensive clinical assessments of included subjects. The overall aim of the project is to assess the primary hypothesis that continuous ECG-monitoring in individuals with elevated NT-pro-BNP and subsequent anticoagulant treatment according to current international guidelines leads to reduced incidence of the composite outcome ischemic stroke and cardiovascular death.

The work performed by the PhD student for which we seek funding by this application will create new knowledge related to:

- 1) the age and sex specific prevalence of various burdens of AF (duration, frequency, heart rate and symptoms) and association with repeated measured risk factors in the Tromsø Study
- 2) the association between AF and echocardiographic parameters
- 3) the association between AF, findings on brain MRI and results of cognitive tests
- 4) participants perception of health-related quality of life before and after AF detection by continuous ECG monitoring

The specific research questions which will be addressed in the present PhD project are:

Question 1: What is the age and sex specific prevalence of paroxysmal AF (considering duration, frequency, heart rate and symptoms) and its association with repeated measured cardiovascular risk factors among Tromsø Study participants with elevated levels of NT-Pro-BNP?

Question 2: Can the presence and burden of AF (duration, frequency, heart rate) in the general population with elevated level of NT-ProBNP be predicted by comprehensive echocardiographic evaluation?

Question 3: Is atrial fibrillation associated with cognitive test performance in subjects with elevated NT-proBNP and is this association modified by specific MRI findings?

Question 4: Does detection of AF by continuous ECG monitoring influence health related quality of life?

The project is planned as a randomized controlled screening trial within the 8th survey of the Tromsø Study (T8), which will be ongoing from March 2025 through 2026. All participants will be invited to complete a questionnaire covering lifestyle, HRQoL, risk factors, as well as simple clinical examinations such as height, weight, ECG, blood pressure, and blood tests. Subsets of up to 10 000 participants will be invited to a second visit to undergo more comprehensive examinations, including extended blood tests with NT-proBNP measurements, cognitive tests, MRI of the brain, and echocardiography of the heart. In the planned trial we aim to include 4000 individuals with NT-proBNP above median without previous known AF or ongoing anticoagulant treatment. Participants will be randomized 1:1 to continuous ECG monitoring using the Norwegian produced ECG247 sensor. ECG247 is an efficient, user-friendly and cost-effective continuous ECG monitor approved for both self-testing and use in health care settings.⁴⁸ The sensor is connected to the

individual participants' smartphone (Bluetooth technology) and has a flash storage if the smartphone is not available. Single lead ECG data is sent to a cloud-based server intermittently. The

Figure 1: Illustration of ECG247 practical setup, modified from www.ecg247.com

system stores information of ECG quality and is evaluated by trained algorithms which classify arrhythmias based on current criteria. The stored data is easily available for the research group, and interpretation, validation, and reclassification if needed. The system fulfills all regulations for a screening tool, as well as handling of sensitive data. Immediate feedback based on an AI based algorithm for analysis will be provided via an app on the participant smartphone if heart rhythm disturbances are detected.

ECG247 has been shown to have

at least as good diagnostic accuracy for AF and improved user-friendliness compared to conventional Holter technology, enables long-term monitoring and can improve the detection of AF.⁴⁸ In most cases, the interpretation is simple and can be performed by other professionals than cardiologists.⁴⁹

The study design enables cross-sectional and longitudinal assessments of associations between AF and repeated measured traditional risk factors, echocardiographic measures, findings on MRI of the brain, and results of cognitive tests. Long term follow-up enables comparison of the group undergoing ECG247 monitoring to those who have not undergone ECG247 monitoring regarding clinical outcomes (after 6 years).

Study population: A total of 4000 individuals from the general population with NT-proBNP > median fulfilling the inclusion criteria will be included after informed consent for study participation.

Inclusion criteria:

- Age ≥40 years
- NT-proBNP > median level
- Informed consent for participation

Exclusion criteria:

- History of AF (self-reported)
- Use of anticoagulation therapy
- Pacemaker/CRT device
- No available smart phone

Study procedure: Individuals with NT-proBNP > median will be identified when attending the second visit of the Tromsø Study. Eligible participants will be included and automatically randomized (1:1) to ECG247 monitoring or no ECG monitoring. Participants not responding will receive two reminders. Invitation will continue until 4000 study participants have been included.

Intervention: The AF screening device will be sent by post from the study centre to all participants in the intervention group at inclusion, free-of-charge. User guides (paper, digital and video) will be prepared (Norwegian and English), and an "help-desk" located at the Tromsø Study will be available for phone/video assistance. The monitoring of included participants will be handled by trained research nurses. All participants will be requested to fill in a digital questionnaire after having completed the test focusing on usability and adverse events. All ECG recordings will be reviewed by a group of trained and experienced study nurses and physicians. Cardiologists will supervise and verify pathologic ECG findings. The following variables will be registered: Heart rhythm (sinus rhythm, AF, atrial flutter, supraventricular tachycardias (SVT),

[figure not shown]

Figure 1: Illustration of ECG247 technical setup, modified from www.ecg247.com

ventricular arrhythmias, SA/AV-block, and other arrhythmias), timing, duration, heart rate of arrhythmias, symptoms and duration of the heart rhythm recording. All study participants will receive information about the test results. A new assessment of HRQoL and medication is planned 6 months post intervention. Initiation and adherence to anticoagulation therapy will be assessed both by questionnaires and by linkage to the Norwegian Prescription Register. Incidence of stroke, cardiovascular and all-cause mortality will be obtained from the Tromsø Study through linkage to national registries.

Safety: In the event of clinically relevant arrhythmias, participants will be contacted as soon as possible. Feedback to the participants will be provided by specially trained physicians and nurses. Participants diagnosed with cardiac arrhythmia or other cardiac abnormal findings will receive advice on follow-up with their general practitioner or be referred to a cardiologist depending of type of arrhythmia. Anticoagulation therapy and other treatments will be recommended if indicated according to current guidelines. The study centre will assist participants who need help to book an appointment for further assessments in cases where this is necessary. An information video about AF will be made in collaboration with the National Association for Heart and Lung Diseases (LHL) to provide general information about AF and potential benefits and risks related to anticoagulant treatment.

Definition of outcomes and other variables of interest: Definition of AF outcome for research question 1 and 2: Paroxysmal AF will be defined as the presence of AF episodes ≥ 30 seconds. In addition, we will register total time in AF (AF burden), beats per minute and concomitant symptoms. Similarly, other tachycardias as atrial flutter (≥ 30 seconds), supraventricular and ventricular tachycardias (cut-offs ≥ 15 seconds and 5 complexes) will also be registered. Initial evaluation will be performed by specially trained research nurses. All positive findings and a similar number of negative tests will be evaluated by a blinded end-point committee of three experts. In case of disagreement the majority will define classification of the outcome.

Cognitive test performance outcome for research question 3: Scores on the 12-word immediate recall test, the digit symbol coding test and the Mini-Mental State Examination (MMS-E). AF outcomes will be as for question 1 and 2. “Health related quality of life (HRQoL)” outcome for research question 4: A single summary index value (utility score) using a predefined scoring algorithm of the HRQoL EuroQol-5 Dimension (EQ5D) and health anxiety using the Whiteley Index. EQ5D is a standardized instrument developed by the EuroQol group to measure HRQoL and consists of two parts a descriptive system comprising five dimensions (mobility, self-care, usual activities, pain/discomfort and anxiety/depression) and visual analog scale measured ranging from 0 to 100 where patients rate their perceived health status, with 0 being "worst imaginable health state" and 100 being "best imaginable health state." Whiteley Index consists of 14 items, and participants respond on a scale from "not at all" to "very much" or similar gradations.

Relevant echocardiographic variables are atrial size (LAVI, Left Atrial volume Index) and atrial strain (LA reservoir strain). Relevant MRI measures are global and segmental atrophy, volume of white matter lesions, size, presence and number of clinical and subclinical infarcts and micro hemorrhages.

Statistics and analyses: The associations between the primary outcome defined as AF presence(yes/no) and AF burden (number of hours with AF) and prespecified risk factors (traditional CVD risk factors and novel echocardiographic measures) will be examined using multiple regression analyses taking repeated measures within individuals into account by the use of generalized linear mixed effect models and linear mixed effect models, respectively. Linear and logistic (binary or ordinal) regression models with adjustment for relevant confounders will be chosen as appropriate when examining the cross-sectional associations between cognitive test performance and HRQoL outcomes and AF depending on the type of outcome variable (continuous, dichotomous or ordinal). Incidences will be reported as the number of events per 100 years at risk. Censoring for the composite outcome will be done at an event, death of other cause or end of follow-up. Hazard ratios (HRs) will be obtained by Cox regression with adjustment for relevant cofactors. Suitable statistical software will be used for analyses and an experienced statistician will be consulted.

Power estimates: Power estimates are customized to test the primary hypothesis that continuous ECG-monitoring in individuals with elevated NT-proBNP and subsequent anticoagulant treatment according to current international guidelines leads to reduced incidence of the composite outcome IS and cardiovascular death. According to a previous study performed at Sørlandet⁵⁰ with ECG247 the number needed to screen was 45 to detect one unrecognized case of AF in subjects at risk for stroke. When restricting screening to the population with NT-proBNP level > median the number needed to screen may be reduced to 31³⁶ and even 23³⁵ in an older population. The 6-year risk of the composite outcome is expected to be 4% in the control group. Risk in the group screened where no AF is found varies from 2 to 3%. In the group screened where AF is found the risk is 10% (30% risk of IS during a 6-year period, reduced by 70% with oral anticoagulant therapy). If the 6-year risk among screened participants without AF is 2.2%, and we include 2000 participants in each group, there is 80% power to detect a significant difference ($\alpha=0.05$) between control and intervention groups with estimated risk of 4.0% vs. 2.4% for the composite outcome, respectively. Based on the results of the Loop and StrokeStop study and the younger population in the Tromsø study, we expect to reduce risk of the composite outcome from 4% in the control group to 2.4% in the screening group. Compared to previous epidemiological studies, the planned epidemiological projects for the PhD student will have sufficient statistical power to explore meaningful associations.

Data handling and storage: EUTRO is a research administrative tool that will be used for data collection and storage in Tromsø 8. EUTRO provides a complete overview of a study's total research material, including responses to questionnaires, biological material, health data, and project information. EUTRO is integrated within TSD (services for sensitive data located at University of Oslo) which assures and facilitates anonymized data handling and storage according to present regulations and research needs. All data security is taken care of according to the requirements from the Norwegian Data Protection Authority, and privacy is well maintained in the system. The system ensures compliance with the Health Research Act and GDPR requirements for security, handling, and administration of sensitive research data and biological material.

Ethics: Separate applications for approval will be sent both for the Tromsø study as a whole and for the present study. Participants must give an informed signed consent before data collection. The study will be conducted in accordance with the Declaration of Helsinki. We will provide relevant feedback to all participants with specific recommendations including how to follow-up positive results. Participants diagnosed with cardiac arrhythmia or other cardiac abnormal findings will receive advice on follow-up. The participant will either be referred to follow-up with their general practitioner or the study team will refer him/her to a cardiologist if indicated. Advise on starting anticoagulant treatment will comply with current guidelines. Appsens AS developed, manufactures and distributes the ECG247 smart heart sensor. Disclosures related to [name] being both employer and shareholder in Appsens, as well as inventor will be handled accordingly. No Appsens-affiliated personnel will be involved in data analyses.

Risks and mitigation: • Patients from the Tromsø 8 study may not be willing to participate. Mitigation: A high percentage of patients invited to follow-up studies in previous Tromsø studies attended. Randomization will continue until the planned number of included participants is met • Patients do not have access to smartphones needed for communication between the sensor and the ECG247 platform. Mitigation: We will provide some smartphones for loan to participants in need in the T8 study. • Too optimistic power calculations if the prevalence of AF is lower than expected and the risk of the composite outcome in the included population is lower than expected. Mitigation: The completion of the PhD thesis is not reliant on collection of the composite outcome at after 6 years follow-up.

Gender perspective: Both women and men will be invited to participate in the study. Analyses will be performed sex-adjusted and/or stratified by sex. The research group consists of both female and male researchers. In line with the project owner's gender policy, women will be encouraged to apply for PhD fellowship and preferred if qualifications are otherwise equal.

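### Question 2 asks whether echocardiography can predict AF, but the matching aim and the stated analysis concern only associations, which cannot answer it.

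*Protocol*

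**What the plan says.** All places are in the Protocol.

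- **Section 1.3, Question 2:** asks whether AF presence and burden in the general population "with elevated level of NT-ProBNP be predicted by comprehensive echocardiographic evaluation".
- **Section 1.3, list of aims, item 2:** describes the same sub-project as "the association between AF and echocardiographic parameters".
- **Section 1.3, Statistics and analyses:** AF presence and AF burden are related to "prespecified risk factors (traditional CVD risk factors and novel echocardiographic measures"), and these associations "will be examined using multiple regression analyses taking repeated measures within individuals into account". Presence is handled by generalised linear mixed models and burden (hours in AF) by linear mixed models.
- **Section 1.3, definition of variables:** "Relevant echocardiographic variables are atrial size (LAVI, Left Atrial volume Index) and atrial strain (LA reservoir strain").
- **Section 1.3, Power estimates:** the PhD projects are said to have enough power for associations; no figure is given.
- **Section 1.2:** the project will "identify biomarkers that would allow stratification of individuals with respect to screening".
- **Section 1.1:** the protocol judges CHA₂DS₂-VASc by its discrimination: its "predictive accuracy is however modest, with a C-statistic of ~0.6 for prediction of thromboembolism".

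**The concern.** Association and prediction are different targets. A regression coefficient says that the average marker value differs between people with and without AF, given the other terms. It does not say how far the two distributions overlap, whether predicted risks are right, or whether the marker improves on what is already known about the person. In a sample of this size a marker can be clearly associated with AF and still sort people poorly.

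Section 1.2 wants markers that help decide whom to screen, which needs evidence on discrimination and added value. Section 1.1 shows that the authors use that standard: they judge the existing score by its C-statistic, and NT-proBNP by whether adding it to the score improved prediction. The analysis stated for Question 2 does neither. What is at stake is a claim that echocardiography predicts AF, resting on an odds ratio.

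**Working it through.** **1. The plan's own figure.** Question 2 has none. The only calculated power in the protocol is for the randomised comparison (2,000 per arm, 4.0% v 2.4%, α = 0.05). It reproduces at 82.0% without continuity correction; with correction, 80% power needs 2,022 per arm. It does not bear on Question 2.

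**2. Expected AF cases.** Only the arm allocated to ECG247 is monitored, so about 2,000 people can contribute. The Power estimates paragraph gives numbers needed to screen of 45, 31 and 23 (the last for an older population):

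- 2000/45 ≈ 44 cases
- 2000/31 ≈ 65 cases
- 2000/23 ≈ 87 cases

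**3. From odds ratio to discrimination.** Assume one marker, normally distributed with equal variance in people with and without AF, and no adjustment. Then C = Φ(ln OR / √2), with OR per SD.

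- OR 1.5: C = Φ(0.405/1.414) = 0.61
- OR 2.5: C = 0.74
- C = 0.60 corresponds to OR = exp(√2 × 0.253) = 1.43

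The odds ratios and C values are my assumptions; the protocol gives none for AF.

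**4. Chance of p<0.05 (two-sided).** With m cases in 2,000, z = ln(OR) × √(m(1 − m/2000)) and power = Φ(z − 1.96). For OR 1.5 and m = 44: z = 0.405 × √43.0 = 2.66, power 76%.

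| AF cases | C = 0.61 (OR 1.5) | C = 0.60 (OR 1.43) | C = 0.60, simulated logistic regression, 1,000 runs |
|---|---|---|---|
| 44 | 76% | 66% | 63% |
| 65 | 90% | 81% | 79% |
| 87 | 96% | 91% | 90% |

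The smallest C that just reaches p<0.05 is about 0.58, 0.57 and 0.56 for 44, 65 and 87 cases.

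**5. What a C of 0.60 is worth for choosing whom to screen.** Take prevalence 1/31 and flag the top half by the marker. Under the same model this half contains 63.6% of the AF cases. The yield among those flagged is (1/31) × 0.636/0.5 = 4.1%, so the number needed to screen falls from 31 to about 24, and some 36% of cases are missed.

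**6. Precision if discrimination is reported.** For C = 0.60 the 95% CI half-width (Hanley–McNeil) is about 0.09, 0.07 and 0.06 for 44, 65 and 87 cases. An interval is therefore essential.

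**7. Room for predictors.** Six terms (four base terms plus two echocardiographic measures) give 44/6 ≈ 7 to 87/6 ≈ 15 cases per term. Ten terms, as when the score's components are entered separately, would give 44/10 ≈ 4 to 87/10 ≈ 9. Performance measured in the data used for fitting will be optimistic, so the model must stay small and be corrected for optimism.

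**The case against.** The strongest reply is that the verb in Question 2 is merely loose. Aim 2, the description of what the design enables, the analysis paragraph and the power statement all speak of association. On that reading one changed word settles the matter. This largely stands, and it is why rewording is offered as a full alternative. It does not remove the inconsistency, because section 1.2 still promises markers for stratifying screening, and association alone does not deliver them.

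A second reply is that C-statistics, calibration and covariate lists belong in a statistical analysis plan, and can be computed from the very regression that the protocol names. That also stands: their absence from the protocol is not the finding. The finding is that the question and the analysis, both stated here, aim at different quantities.

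Three stronger readings may tempt a reader, and the documents do not support them:

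- **That any significant marker would be reported as a predictor.** The protocol sets no such rule. It could happen; it is not planned.
- **That the C-statistic of about 0.6 in section 1.1 is the bar echocardiography must clear.** That figure is for thromboembolism. No C-statistic for AF is given, so it only exemplifies weak discrimination.
- **That NT-proBNP has been left out of the model.** The analysis paragraph names two broad groups of risk factors, not a model specification, and everyone enrolled is already above the median. It can only be said that the text does not ensure that added value over the NT-proBNP level is shown.

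The illustration is also favourable to finding significance. Adjustment, or missing echocardiography or recordings, would lower the power, and the 87-case figure relates to an older population while the protocol calls the Tromsø population younger. Lower power would not turn an association into a prediction.

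**Conclusion.** The point holds as a mismatch between a prediction question and an association analysis, both stated in section 1.3. Under the assumptions above (one unadjusted normal marker, complete data on about 2,000 people, 44 to 87 cases), a marker with C of 0.60 to 0.61 for AF would be significant in roughly 63% to 96% of studies. A significant coefficient is therefore weak evidence of useful prediction. The conclusion that association does not answer a prediction question needs none of these numbers; they show only how easily the two could be confused here.

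The reach is limited. This is one of four secondary PhD questions, and nothing in it touches the randomised comparison of ischaemic stroke and cardiovascular death.

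**What to change.** Choose one of two routes before AF results are known.

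**If prediction is intended:**
- **AF presence:** among monitored participants who have echocardiography, compare a small base model (for example age, sex, log NT-proBNP and CHA₂DS₂-VASc as a single score) with the same model plus LAVI and LA reservoir strain. Report the change in C-statistic with 95% CI and the calibration, both bootstrap-corrected for optimism. State how many monitored participants had echocardiography, since the protocol does not guarantee it for all.
- **AF burden:** a C-statistic for presence does not answer this half. Report an optimism-corrected measure of explained variation or prediction error, or limit the claim to association.
- Keep the regression coefficients as description.

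**If prediction is not intended:** reword Question 2 to ask about association, in line with aim 2, and limit the stratification claim in section 1.2 to match.

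**Cost:** the first route takes a little more analysis on data planned for the second visit and may give a less favourable result than a significant odds ratio. The second is an edit to the text and a more modest claim.
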